# 9.4 Handling of Expedited Safety Reports

In accordance with local regulations, the Protocol Chair or designee will notify investigators of all SAEs that are unexpected (i.e., not previously described in the IB), and related to olaparib and IV ascorbic acid. This notification will be in the form of an expedited safety report (ESR) that is to be faxed to the investigators and the study coordinators. Upon receiving such notices, the investigator must review and retain the notice with the IB and where required by local regulations, the investigator will submit the ESR to the appropriate IRB. The investigator and IRB will determine if the informed consent requires revision. The investigator should also comply with the IRB institutional guidelines for reporting any other safety information.

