# 4.2 Treatment Background

#### 4.2.1 Description and mechanism of action of Olaparib

PARP functions in the DNA repair pathway, specifically by serving in base excision repair of DNA single strand breaks. Inhibition of PARP results in inability for cells to repair single strand breaks. Cells normally would employ the error-free homologous recombination pathway to repair such defects. However, in tumors that harbor defects in these DNA repair genes (such as BRCA1/2), the strand breaks lead to chromosomal instability and eventually cell death. Olaparib functions in cells to inhibit various isoforms of PARP.

Investigators should be familiar with the current olaparib (AZD2281) Investigator Brochure (IB).

[figure not shown]
Olaparib (AZD2281, KU-0059436) is a potent polyadenosine 5'diphosphoribose [poly (ADP ribose)] polymerization (PARP) inhibitor (PARP-1, -2 and -3) that is being developed as an oral therapy, both as a monotherapy (including maintenance) and for combination with chemotherapy and other anti-cancer agents. Olaparib [Lynparza] was approved by the FDA for treatment of men with prostate cancer who have deleterious or suspected deleterious germline or somatic homologous recombination repair gene-mutated metastatic castration resistant prostate cancer who have progressed on Abiraterone or Enzalutamide.

PARP inhibition is a novel approach to targeting tumors with deficiencies in DNA repair mechanisms. PARP enzymes are essential for repairing DNA single strand breaks (SSBs). Inhibiting PARPs leads to the persistence of SSBs, which are then converted to the more serious DNA double strand breaks (DSBs) during the process of DNA replication. During the process of cell division, DSBs can be efficiently repaired in normal cells by homologous recombination repair (HR). Tumors with HR deficiencies (HRD), such as ovarian cancers in patients with BRCA1/2 mutations, cannot accurately repair the DNA damage, which may become lethal to cells as it accumulates. In such tumor types, Olaparib may offer a potentially efficacious and less toxic cancer treatment compared with currently available chemotherapy regimens.

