
Intravenous ascorbic acid is in wide use by practitioners of complementary and alternative medicine. Estimates are that in the US approximately 10,000 patients receive IV ascorbic acid each year at average doses of 0.5/kg, with average number of doses of twenty per patients. Using multiple tracking mechanisms, minimal adverse events were reported in properly screened patients.

**4.2.8 Clinical efficacy and safety of combination Olaparib and IV Ascorbate** This trial seeks to assess the combination of olaparib and IV ascorbic acid in men with castration resistant prostate cancer. There is no clinical data to support this combination at this time as these two agents have not been combined in the past to treat castration resistant prostate cancer. The CRPC patient population is in desperate need of new treatment options, and the *in vitro* and *in vivo* data suggest that the combination of olaparib and ascorbate may be effective. The proposed clinical trial aims to determine the safety, tolerability, and provide preliminary data on efficacy of combining olaparib with intravenous ascorbate for the treatment of advanced prostate cancer.

A drug-drug interaction between ascorbic acid and olaparib is not anticipated based on drug metabolism and drug transporters. Olaparib metabolism is primarily mediated by CYP3A4/5. Clinical drug-drug interactions have been noted with strong or moderate CYP3A4 inhibitors or a moderate CYP3A4 inducer. Olaparib is a substrate for Pgp. Olaparib is an inhibitor of CYP3A4, UGT1A1, Pgp, OATP1B1, OCT1, OCT2, OAT3, MATE1, and MATE2K in vitro. Olaparib is an inducer of CYP1A2, CYP2B6 (potentially clinically relevant), CYP3A4, and P-gp. Ascorbic Acid is reversibly oxidized to dehydroascorbic acid (DHA) and metabolized to inactive compounds including ascorbic acid-2-sulfate and oxalic acid. No drug interactions have been noted via the CYP450 pathway. Ascorbic acid is a substrate of two sodium-ascorbate co-transporters (SVCT; both members of the SLC23 family). Oxalic acid is a substrate of OAT3 and inhibitor of OATP1B1. There is a potential for an interaction via the drug transporters at the oxalic acid level but would not be anticipated to be clinically relevant. Therefore, a formal pharmacokinetic assessment will not be conducted.

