#### 9.2.1 Expected Adverse Events

Expected adverse events are those that have been previously identified as resulting from administration of the agent. An adverse event can be considered expected when it appears in the current adverse event list, the Investigator's Brochure, the package insert or is included in the informed consent document as a potential risk.

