# 9.2.2 Unexpected Adverse Events

An adverse event can be considered unexpected when it varies in nature, intensity or frequency from the information provided in the current adverse event list, the Investigator's Brochure, the package insert or when it is not included in the informed consent document as a potential risk. Contact the lead site, Principal Investigator or sponsor to confirm unexpected adverse events when necessary.

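### The Section 9.4 trigger for expedited safety reports omits the intensity and frequency test of Section 9.2.2, does not say which Investigator's Brochure applies, and is ambiguous for an SAE attributed to one drug

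*Combined protocol and SAP*

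**What the plan says.** Three provisions bear on expectedness.

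- **Section 9.2.1** calls an event expected when it "appears in the current adverse event list, the Investigator's Brochure, the package insert or is included in the informed consent document". One source is enough, and severity and frequency play no part.
- **Section 9.2.2** gives two grounds for calling an event unexpected. The first is that the event "varies in nature, intensity or frequency from the information provided in the current adverse event list, the Investigator's Brochure, the package insert". The second is that the consent form does not name it among the possible risks; this alone is sufficient.
- **Section 9.4** has the Protocol Chair or a designee notify investigators of "all SAEs that are unexpected (i.e., not previously described in the IB), and related to olaparib and IV ascorbic acid". The investigator must review and keep the notice and, where local rules require, send it to the IRB. The investigator and the IRB then decide whether the consent form needs revision.

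Two brochures exist: Section 4.2.1 cites one for olaparib and Section 4.2.4 one for ascorbic acid. Section 9.4 refers to a single, unnamed IB. The forms in Appendices B and F have separate related/unrelated entries for olaparib, IV ascorbic acid and underlying disease. On earlier experience with the two drugs together, Section 4.2.8 states: "There is no clinical data to support this combination at this time".

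**The concern.** When two drugs with known profiles are combined for the first time, a plausible safety signal is a known toxicity that becomes worse or more common. Section 9.2.2 is written to catch that. Section 9.4 is the rule that sends a written alert to the other sites of this multi-center trial, and its own gloss on unexpected leaves that kind of event out. Section 9.4 is also where the plan ties a notice to a decision on revising consent, so an event outside it does not prompt that decision by this route.

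The relatedness clause raises a second question. If it means both drugs at once, a wholly new SAE attributed to one drug falls outside the rule, even though the forms allow exactly that attribution.

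**Working it through.** No figure in the plan needs reproducing. The check sets the rules side by side and counts the logical cases.

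**Particular cases**

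| SAE | 9.2.1 | 9.2.2 | 9.4 report required? |
|---|---|---|---|
| Listed in all four sources, worse than listed, related to both drugs | Expected | Unexpected | No |
| In the IB but not the consent form, no worse than listed, related to both drugs | Expected | Unexpected | No |
| Listed nowhere, related to one drug only | Not expected | Unexpected | Only if the clause means either drug |

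**Enumeration.** Use four yes/no flags for listing (adverse event list, IB, package insert, consent form) and one for being worse than, or different from, what is listed. That gives 2^5 = 32 combinations. Section 9.2.2 can be read in two ways:

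- *Wide:* absence from the adverse event list, IB or package insert itself counts as differing in nature.
- *Strict:* only differing from a listing, or absence from the consent form, counts.

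Combinations counted as unexpected:

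- Complement of 9.2.1 (in no source): 2.
- 9.4 (not in the IB): 16.
- 9.2.2 strict: 16 (not in consent) + 8 (in consent but worse) = 24.
- 9.2.2 wide: 32 − 1 (in all four and no worse) = 31.

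Both expected under 9.2.1 and unexpected under 9.2.2: 24 − 2 = 22 (strict) or 31 − 2 = 29 (wide).

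Unexpected under 9.2.2 but outside 9.4, among the 16 combinations listed in the IB: 8 (not in consent) + 4 (in consent but worse) = 12 (strict), or 16 − 1 = 15 (wide).

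The strict reading also has a reverse gap. An event absent from the IB, present in the consent form and no worse than listed (4 combinations) is unexpected under 9.4 but not under 9.2.2. The fix must not lose these.

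**Which IB.** Section 7.9.1 lists renal failure for ascorbic acid; Section 7.9.2 lists only raised creatinine for olaparib. If the two IBs follow these lists (an assumption, since neither is in the documents), renal failure is described in one and not the other, and 9.4 gives no answer.

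**One drug or both.** Exposure to one drug alone is part of the plan. The calendar footnote in Section 7.1 and Section 7.6.2 have olaparib given alone in week 1, with ascorbic acid starting on cycle 1 day 8. (The calendar grid also marks ascorbic acid on cycle 1 day 1; those entries need reconciling in any case.) Section 8.1 lets either drug continue while the other is held. Section 9.3.3 makes an event related only if no other cause, including concomitant drugs, can be identified. If the partner drug counts as concomitant, relatedness to both would be hard to record.

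**The case against.** The strongest reply is that other safeguards do not use the 9.4 test. Section 9.5.1 sends every SAE, whatever its expectedness, to the IND sponsor, the Protocol Chair and both companies within 24 hours. Section 12.2 provides monthly calls with the sites that cover safety data, and Section 12.3 adds a Safety Monitoring Committee. Section 13.6 has a continuous toxicity rule and a pause for any event of special interest. Section 9.4 itself refers to local regulations and to IRB guidelines for other safety information, and Section 9.2.2 sends doubtful cases to the lead site, Principal Investigator or sponsor. This stands against any inference that sites would hear nothing: what is missing is the required expedited report.

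These routes do not fill the gap. The 24-hour reports run inward to the sponsor and companies. The calls can come weeks later, and Section 12.2 attaches no IRB or consent step to them. The pause covers MDS/AML, new primary malignancy and pneumonitis; the toxicity rule counts grade 3-4 events that fail to resolve to grade 2 after four weeks off drug. A severe renal event that resolves meets neither.

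It is also fair to say that the relatedness clause may simply name the regimen, and that Sections 9.2.1 and 9.2.2 are phrased permissively. The first makes the clause ambiguous rather than a proven exclusion. The second does not help, because the gloss in 9.4 is stated as a definition.

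**Conclusion.** The conflict is real and should be corrected. Followed as written, 9.4 requires no expedited report for an SAE that the IB describes but that is worse or more frequent than described; 9.2.2 calls that event unexpected and 9.2.1 calls it expected. The IB reference and the relatedness clause are each open to two readings. The case counts show how far the definitions diverge, not how often events would be missed; the documents give no basis for such a rate. No sample size, error rate or analysis is affected.

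Four stronger inferences are not supported:

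- **That 9.4 is the narrowest test of expectedness.** The complement of 9.2.1 is narrower (2 combinations against 16).
- **That the plan has three definitions of unexpected.** Only 9.2.2 and 9.4 define it; 9.2.1 defines expected.
- **That the conflict slows SAE reporting,** because Section 9.5.1 refers to unanticipated events in its Coordinating Center timeline. The same section makes every SAE due to the sponsor and Protocol Chair within 24 hours.
- **That the toxicities shared by 7.9.1 and 7.9.2 measure what would go unreported.** The 9.4 trigger does not turn on overlap, and the IB contents are unknown.

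**What to change.** 1. In Section 9.4, replace the gloss on unexpected with a reference to Section 9.2.2, judged against both the olaparib and the ascorbic acid IBs. State that absence from the IB counts as differing in nature, so that nothing 9.4 now covers drops out, and say how an event described in only one IB is treated.
2. In Section 9.4, reword the relatedness clause to cover an SAE related to olaparib, to IV ascorbic acid, or to both.
3. In Section 9.2, keep the intensity and frequency test of 9.2.2 and define expected as its complement, so that no event is both. The reverse, making unexpected the complement of 9.2.1, would delete the test that needs to be kept.

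The cost is a few lines of wording and possibly a few more safety notices in a trial of 12 to 15 men.

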# 9.5 Reporting Adverse Events

# **9.5.1 Reporting Adverse Events (AEs) and Serious Adverse Events (SAEs)** All AEs (both expected and unexpected) occurring from the first dose of study drug

All AEs (both expected and unexpected) occurring from the first dose of study drug will be captured on the appropriate study-specific case report forms (CRFs).

All AEs experienced by subjects will be collected and reported from the first dose of the investigational agent, throughout the study, and will be followed for 30 days after last dose of study drug unless related to the investigational agent.

All SAEs (including death) occurring from the first dose study drug, throughout the study, and 30 days after the last dose of study drug or before initiation of a new antineoplastic treatment (whichever comes first) must be reported. All SAEs that the investigator considers related to the study drug occurring after the follow-up periods must be reported.

In addition, all SAEs, regardless of causality to study drug and/or administration device, will be reported promptly to the IND sponsor (e-mail: [contact], [contact] ), and [contact], within 24 hours of recognition of the event (Appendix B). If this falls on a weekend or holiday, an email notification is acceptable but must be followed by an SAE reporting form on the next business day.

### **Coordinating Center**

The Coordinating Center is the central location for the collection and maintenance of documentation of adverse events and is responsible for submitting adverse event reports to the Protocol Chair promptly. The Coordinating Center will maintain documentation of all adverse event reports for each participating site. Adverse event reports submitted to the Coordinating Center must be signed and dated by the participating site's Principal Investigator. The Coordinating Center will provide appropriate forms to be used by all participating sites for reporting adverse events. Information to be provided must include:

- Subject ID number, and initials
- Date of the event
- Description of the event
- Description of site's response to the event

- Assessment of the subject's condition
- Subject's status on the study (on study, off study, etc.)
- Attribution of event to study drug

## **Participating Sites**

Participating sites are responsible for reporting adverse events to their IRB according to its specific requirements and to the Coordinating Center as follows:

**Fatal Events** whether anticipated or unanticipated, and whether or not related to the study must be reported to the Coordinating Center within **24 hours** of the participating site Principal Investigator's learning of the event.

**Serious and Unanticipated Adverse Events** as defined above must be reported to the Coordinating Center within **24 hours** of the participating site Principal Investigator's learning of the event.

**Other Serious Adverse Events** which may result in a change to the protocol, informed consent, or risk to subjects as specified in the protocol must be reported within **three (3) working days** of the participating site Principal Investigator's learning of the event.

Adverse Events which result in no change to protocol, informed consent, or risk to subjects must be reported to the Coordinating Center on a monthly basis.

Adverse event reports are to be faxed to the Coordinating Center at SKCCC. Follow-up reports are faxed, mailed, or sent electronically to the Coordinating Center as necessary.

The investigator must also report follow-up information about SAEs within the same time frames.

If a non-serious AE becomes serious, this and other relevant follow-up information must also be provided within the same time frames described above.

All SAEs must be collected whether or not they are considered causally related to the investigational product. Investigators and other site personnel are responsible for reporting all casually related SAEs to their IRB and the Protocol Chair.

Although pregnancy and lactation are not considered AEs, it is the responsibility of investigators or their designees to report the pregnancy of a male patient's female partner within 4 weeks days of completing the trial. All pregnancies of female partners of patients must be followed to the completion/termination of the pregnancy. Pregnancy outcomes of spontaneous abortion, missed abortion, benign hydatidiform mole, blighted ovum, fetal death, intrauterine death, miscarriage, and stillbirth must be reported as SAEs (Important Medical Events). If the pregnancy continues to term, the outcome (health of infant) must also be reported to the IND sponsor, CRO, McGuff and AZ.

Report AEs to the Protocol Chair and CRO within 24 hours once identified as an unacceptable toxicity (defined in Section 8.1).

Report Olaparib AESIs to Lead Study Coordinator, Protocol Chair, and AstraZeneca within 24 hours once identified (defined in Section 9.1.3) using the form found in Appendix F.

[name] (Protocol Chair): [contact]

[name] (Monitor): [contact]

AstraZeneca: [contact]

[contact]

All SAEs (including death) occurring from the first dose study drug, throughout the study, and 30 days after the last dose of study drug or before initiation of a new antineoplastic treatment (whichever comes first) must be reported. All SAEs that the investigator considers related to the study drug occurring after the follow-up periods must be reported.

SAEs will be reported promptly to the Protocol Chair, AstraZeneca, and McGuff within 24 hours of recognition of the adverse event using the form found in **Appendix B**. If this falls on a weekend or holiday, an email notification is acceptable but must be followed by an SAE reporting form on the next business day.

SAE reports and any other relevant safety information are to be sent to:

[name] (Monitor): [contact]

[name] (Protocol Chair): [contact]

AstraZeneca: [contact]

[contact]

McGuff: [contact]

### 9.5.2 Follow-up of Adverse Events and Serious Adverse Events

After the initial AE or SAE report, the investigator is required to proactively follow each subject and provide further information to the safety department concerning the subject's condition.

All AE(s) and SAE(s) will be followed until:

- Resolution
- The condition stabilizes
- The event is otherwise explained

- The subject is lost to follow-up
- Death

As soon as relevant information is available, a follow-up SAE report will be submitted to the Protocol Chair, Monitors, AstraZeneca, and McGuff.

#### 9.5.3 Reconciliation of SAEs

The Principal Investigator will reconcile the clinical database SAE cases (case level only) transmitted to Monitors, AstraZeneca ([contact]), and McGuff ([contact]). Frequency of reconciliation should be approximately every 3 months and prior to the database lock or final data summary. AstraZeneca and McGuff will email, upon request from the Principal Investigator, the reconciliation report. The data elements listed on the AstraZeneca reconciliation report will be used for case identification purposes. If the Principal Investigator determines a case was not transmitted to the Protocol Chair, Monitors, AstraZeneca, and McGuff, the case should be sent immediately to the Protocol Chair, Monitors, AstraZeneca, and McGuff.

### 9.5.4 Institutional Review Board (IRB)

Participating sites will be responsible for reporting to their IRB. Serious adverse events will be reported to the IRB per institutional standards. Upon receipt, follow-up information will be given to the IRB (as soon as relevant information is available) per institutional standards.

## 10.0 PHARMACEUTICAL INFORMATION

#### 10.1 Ascorbic Acid

# 10.1.1 Agent Accountability

The sponsor/investigator shall take responsibility for and shall take all steps to maintain appropriate records and ensure appropriate supply, storage, handling, distribution, and usage of investigational products in accordance with the protocol and any applicable laws and regulations.

#### 10.1.2 Mode of Action

Ascorbic Acid (vitamin C) is a water-soluble vitamin. In humans, an exogenous source of ascorbic acid is required for collagen formation and tissue repair. Ascorbic acid is reversibly oxidized to dehydroascorbic acid in the body. These two forms of the vitamin are believed to be important in oxidation-reduction reactions. The vitamin is involved in tyrosine metabolism, conversion of folic acid to folinic acid, carbohydrate metabolism, synthesis of lipids and proteins, iron metabolism, resistance to infections, and cellular respiration.

### 10.1.3 Description

Ascor L 500® (Ascorbic Acid Injection, USP) 500mg/mL, is available in a 50-mL sterile dispensing vial. Ascorbic Acid injection is a clear, colorless to slightly yellow sterile, solution of Ascorbic Acid in Water for injection.

# 10.1.4 Preparation

When dispensing vials, use aseptic technique. Dispense entire contents in aliquots under a laminar flow hood without delay. Prepare stoppers with a suitable antiseptic technique. Do not use unless solution is clear and seal is intact. Parenteral drug products should be inspected visually for particulate matter and discoloration prior to administration, whenever the solution and container permit. Ascorbic acid should be diluted in sterile water for injection (final volume of 1000ml).

The ascorbic acid for infusions will be prepared by the pharmacy. The calculated dose of ascorbic acid will be diluted in Sterile Water for injection USP.

A study-specific worksheet will be completed when preparing ascorbic acid infusions. The worksheet will document the dose prepared and calculations for dose preparation.

